1. Smoking cessation medication (e.g., Zyban, Wellbutrin, Wellbutrin SR, Chantix);
2. Anti-psychotic medications;
3. Nicotine replacement therapy (NRT);
4. GABAergic medications;
5. Glutamatergic medications;
6. Any medication that could compromise participant safety as determined by the Principal Investigator and/or Study Physician.

Daily use of:

7. Opiate-containing medications for chronic pain;
8. Benzodiazepines.

**Medical/Neuropsychiatric:**

1. Women who are pregnant, planning a pregnancy, and/or breast feeding. All female subjects will complete a urine pregnancy test at the intake visit and preceding all brain stimulation sessions (4 urine pregnancy tests in total). Women who self-report a condition which renders them unable to become pregnant (i.e., hysterectomy, surgical sterility, menopause, etc) will not be required to complete the pregnancy tests;
2. History of epilepsy or a seizure disorder;
3. History of stroke;
4. Self-reported history of brain or spinal tumor;
5. Self-reported history or current diagnosis of psychosis, including schizophrenia, mania, bipolar disorder, major depression (subjects with a history of major depression but in remission for past 6 months are eligible).

**tDCS-related:**

1. Self-report of metallic objects in the face or head **other than** dental apparatus (e.g. braces, fillings, and implants);
2. Self-report of pacemakers or implantable cardioverter-defibrillator (ICD).
3. Self-report of any skull fracture or opening.

**Note:** In contrast to Transcranial Magnetic Stimulation (TMS), there is no known risk of seizures with tDCS. However, the individuals with self-reported history of epilepsy, a seizure disorder, or any seizure in the last 6 months will be excluded. Similarly, although there is no known risk of tDCS to the fetus, the issue has not been fully addressed. Consequently, pregnant women will be excluded. All women of childbearing age (that is, not post-menopausal, surgically sterile, or otherwise unable to become pregnant) will complete a pregnancy test prior to each tDCS session.

**General Exclusion:**

1. Any medical condition, illness, disorder, or concomitant medication that could compromise participant safety or treatment, as determined by the Principal Investigator;
2. Low or borderline intellectual functioning – determined by a score of less than 85 on the Shipley Institute of Living Scale (SILS) (administered at Intake Visit). The SILS correlates with the Wechsler Adult Intelligence Scale-Revised (WAIS-R) Estimated IQ Test;
3. Inability to provide informed consent or complete any of the study tasks as determined by the Principal Investigator.

***5. Vulnerable Populations***

Children (under age 18), pregnant women or prisoners are not included in this research study.

***6. Populations vulnerable to undue influence or coercion***

Educationally or economically disadvantaged persons are included but not solely targeted for recruitment. Cognitively impaired persons are not included in the current study. Because of our recruitment efforts for this study, it is possible that University of Pennsylvania employees and students may be invited to participate. Status of participation in the current study will be independent of the participant's work or school activities.

***7. Subject Recruitment***

Participants may be recruited from television, radio, Craigslist.org/Internet advertisements, experiments@penn, newspaper, iConnect, flyers, University of Pennsylvania Human Resources (HR) communication vehicles (e.g. Penn Current, myHR Newsletters, hr.upenn.edu, etc.), and/or from our database of previous participants who have agreed to be re-contacted for future studies. Participants initially eligible during a telephone screening will attend an Intake Visit at our center during which the purpose and procedures of this study will be described to them and final eligibility will be confirmed.

## STUDY DESIGN

### 1. Phase

Not applicable

[figure not shown]
### 2. Design

This trial will use a between-subject single blind design in which participants will be randomized to one of three tDCS dosage groups (1mA, 2mA or sham) and will receive three 20 minute sessions of the same dosage over the course of 1 week before completing a 7 day quit attempt. Eligible participants will complete an **Intake Visit (week -1)** for final eligibility determination, and complete baseline measures (if eligible). Participants will then be randomly assigned to one of the three dosage groups (1mA, 2mA or sham) and will attend **three identical tDCS resist-smoking sessions (study days 1, 3, & 5)** during which they will receive 20 minutes of their assigned tDCS dosage and complete a resist smoking paradigm. During the resist smoking sessions, participants will receive a session of their assigned dosage of tDCS for 20 minutes while being exposed to in vivo smoking cues (their cigarette pack, cigarettes, an ashtray). Participants will not be informed of their dosage condition. During and after the tDCS session, participants will have the opportunity to smoke in the approved smoking lab. We will measure time to first cigarette and subsequent ad-libitum smoking during the resist smoking paradigm. Following Session 3 participants will receive a 20 minute coaching session from a trained smoking cessation counselor to help them prepare for a **7-day quit attempt**. During the 7-day quit attempt participants will be asked to attend **4 monitoring visits (study days 6, 8, 10 & 12)** to confirm smoking status.

### 3. Study Duration

Enrollment began in October 2015. Based on the accrual projections described previously, we anticipate enrollment lasting through March 2018 (~25 months). Each participant will be required to be in the study for approx. ~3-4 weeks.

**Figure 1.**

## DRUGS OR DEVICES

## Transcranial direct current stimulation (tDCS) and sham stimulation.

## STUDY PROCEDURES

## 1. Procedures

**Telephone Screening:** Potential participants will be screened by an experienced research technician to determine initial study eligibility. If the subject meets preliminary telephone eligibility criteria he/she will be invited to attend a 3 hour Intake visit.

**Visit Reminders:** Participants will receive study visit reminders 24 – 48 hours prior to their scheduled study visits via phone call, email or text (participants who provide a cell phone number for contact).

**Intake (week -1):** (Visit duration: ~3 hours). Participants will:

1. Hear a study description where all study procedures will be reviewed. Participant questions will be answered. Following this presentation, the combined informed consent and HIPAA form will be completed;
2. Women of childbearing potential will be provided with a urine pregnancy screen and will be instructed to perform the screening independently Participants will be instructed that women who think they are pregnant are advised not to participate in the study;
3. Perform a BrAC assessment to control for alcohol consumption. Participants with a BrAC greater than or equal to 0.01 at Intake Visit will be ineligible;
4. Perform a carbon monoxide (CO) breath assessment to confirm ( $CO \geq 10$  ppm) tobacco exposure;
5. Complete a brief medical history form with a trained staff member;
6. Complete Shipley Institute of Living Scale (SILS) IQ test. Participants earning less than an estimated WAIS-R IQ score of 85 will be ineligible;
7. Complete demographics and smoking history (smoking rate, nicotine dependence, Cigarette Brand Form, brief QSU), G-FCQ-S, ETOH, and cognitive tasks (see Measures table);
8. Provide one 2ml saliva sample for DNA collection and genotyping (Oragene™) and a 5ml saliva sample for nicotine metabolite assay. These saliva samples are voluntary for study participation.

**tDCS Sessions:** (Visit duration ~3 hours). The stimulation protocol is adapted from IRB protocol 809185 (Transcranial Direct Current Stimulation Investigations of Cognition and Action), which was employed in The Laboratory for Cognition and Neural Stimulation (LCNS) and protocols 820231, 819023 & 820371 at CIRNA.

Participants will complete stimulation sessions on Days 1, 3, & 5 (**week 1**). Participants will receive a call instructing them to stop smoking ~18 hours before their tDCS Session 1, tDCS Session 2, and tDCS Session 3 appointment start times (resulting in ~18 hours of smoking abstinence at the start of these visits).

Participants will complete the following prior to the tDCS period:

1. Women of childbearing potential will be provided with a urine pregnancy screen and will be instructed to perform the screening independently. Participants will be instructed that women who think they are pregnant are advised not to participate in the study;
2. BrAC assessment. See breath alcohol concentration under screening/covariates for exclusionary criteria;
3. Carbon monoxide (CO) Breath sample (must be <10 ppm or 50% of intake CO level at Session 1 to participate).
4. Paper and pencil questionnaires (brief QSU-B, G-FCQ-S, smoking TLFB).

**tDCS Training Procedures:** Prior to each tDCS period an investigator or trained research assistant will review the procedures, goals, risks, and potential benefits of the study and confirm that no change has occurred affecting study inclusion and exclusion criteria. The tDCS sessions will be conducted by a trained technician using the neuroConn DC-Stimulator Plus system. Participants will receive sham or active tDCS using the parameters described below. The participant will be blind to condition (sham vs. active and dosage).

Active tDCS: A neuroConn DC-Stimulator Plus will apply a constant direct current (1.0 mA to 2.0 mA via 5x7 electrode) to the left dorsal lateral prefrontal cortex. Each participant will receive anodal stimulation for a period of 20 minutes. For anodal stimulation over the left DLPFC, the anodal electrode will be placed over the left F3 and the cathodal electrode over the right supraorbital area (international EEG 10/20 system).

**Sham tDCS:** During sham tDCS, a 1.0 mA to 2.0 mA current will be delivered for approximately 30 seconds before being extinguished over a course of seconds. Again, the anodal electrode will be placed over the left F3 and the cathodal electrode over the right supraorbital area. Most participants cannot distinguish between real and sham tDCS (Gandiga, Hummel et al. 2006).

**tDCS Safety:** Although neuroConn DC-Stimulator Plus is not FDA-approved, the tDCS procedures described above have been considered to pose a minimal risk by the University of Pennsylvania IRB (protocol 809185 in normal controls, 811842 in stroke patients, 814366 in patients with neglect, 818662 in patients with Primary Progressive Aphasia, 819023 in normal controls and healthy smokers, and 820231 in healthy smokers). A literature search on the topic of tDCS in healthy individuals, smokers, stroke patients, dementia, and neurologic diseases indicates a lack of adverse events or significant risks in these populations (for detailed discussion of safety see RISK/BENEFIT ASSESSMENT below). Although adverse effects are considered unlikely to occur, a physician will always be within a 5 minute transit time of the subject during any tDCS application.

**Craving and Smoking Assessment:** Following the protocol developed and validated by Sherry McKee at Yale University (McKee 2009), the smoking lapse paradigm will be conducted as follows:

1. Participants will be placed in a CIRNA laboratory 10 x 10 room equipped with industrial grade exhaust fans designed and approved for exhaust of cigarette smoking; a comfortable chair; and viewing windows to observe participants.
2. Eight cigarettes of their preferred brand will be placed in view on a table in the lab room along with a lighter and ashtray. Prior to initiating the tDCS session, they will be informed that over the next 50 minutes "you can start smoking at any time, but for each 5 minute period that you are able to delay, you earn \$1.00 for a maximum of \$10.00." They will also be told "once you decide to smoke, you may smoke as little or as much of these cigarettes as you wish." They will be instructed that there is a set time for discharge to avoid them ending the resist period early, thinking they will be discharged early. Once instructions have been delivered the 20 minute tDCS session will begin. The tDCS headgear will remain in place until the end of the 50 minute resist period to avoid influencing the participant's smoking behavior; however, the stimulation will only be delivered for the first 20 minutes. Smoking sessions will be video recorded to capture smoking behavior (i.e. time to first cigarette, number of cigarettes smoked). These video recordings will be destroyed after they have been transcribed.
3. After 50 minutes (regardless of whether the participant decided to smoke during the resist period), the 60 minute ad-lib smoking session will commence. During this period, participants will receive \$4.00 at the beginning of the session and will be instructed to "smoke as much or as little as you wish." They will be further instructed that for each cigarette lit, they would "lose \$0.50 from their \$4.00 tab." The primary outcomes will be latency to first cigarette and number of cigarettes smoked during the resist and ad-lib periods.
4. At the end of the ad-lib period, all participants will be asked to smoke one cigarette in order to standardize smoke exposure for subsequent tasks.
5. Participants will complete paper and pencil assessments of craving and a tDCS side effects questionnaire.

At the end of Session 3, smokers will receive a 20-minute in person coaching session and be instructed to try to remain abstinent from 10 P.M. that evening until after the final Monitoring Visit (7 days of monitored abstinence), with small monetary incentives for abstinence and biochemical verification. All participants will be discharged ~4 hours after their appointment start time.

**Monitoring Visits:** (Visit duration ~20 minutes). During the monitored abstinence period, participants will complete 4 Monitoring Visits (days 6, 8, 10, and 12). Participants will be given instructions to remain abstinent from smoking from 10 P.M. the evening of Day 5 until after they complete their final Monitoring Visit on Day 12. On Days 6, 8, 10, and 12, all participants will be asked to come to the CIRNA for brief visits to complete the following:

- Complete CO, smoking rate (TLFB), and concomitant medication assessment.
  - To increase abstinence motivation, participants will receive \$15/day (in cash) for each day of self-reported abstinence that is biochemically-confirmed. On Day 6, a CO reading of less than 10ppm or less than 50% of CO breath sample taken at the Intake session will be sufficient as

biochemically-confirmed abstinence. On Days 8, 10, and 12, a CO reading less than 8 ppm will be considered as biochemically-confirmed abstinence.

- Complete measures of smoking urges (Table 1).

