**Table 1. Measures and Time Points**

Activity	Intake	tDCS Sessions 1-3	Monitoring Visits 1-4
Weeks	-1	0	1
Urine Pregnancy Screen	x	x	
BrAC	x	x	
Time Line Follow Back (TLFB), CO	x	x	x
Demographics	x		
ETOH History	x		
Height	x		
Weight	x		
Medical History Form	x		
Shipley Institute of Living Scale (SILS)	x		
Saliva for DNA (Oragene™)	x		
Saliva sample (for nicotine metabolites)	x		
Smoking Behavior (FTND & Cigarette Brand)	x		
Treatment/Training			
tDCS (1mA, 2mA or sham)		x	
Side effects		x	
Intermediate Outcomes			
Urges/Cravings (QSU-B)	x	x	x
Post-Test Questionnaire		x*	
Primary Outcomes			
Ability to Resist Smoking		x	
Number of Puffs, Cigarettes		x	
Days of biochemically confirmed abstinence			x

\*after session 3 only

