### 1. Screening/Covariates:

**Urine Pregnancy Test (females only):** At the Intake and Session 1-3 visits (4 urine pregnancy screens total), participants will be supplied with a simple, CLIA-waived urine pregnancy screen and informed that pregnant women are not advised to participate in this research study. Participants will then be instructed to administer the pregnancy test independently and will inform study staff if they would like to continue participation after they have administered the pregnancy screen. Participants will be informed that there is no penalty for discontinuing participation at this point in the visit and that they will still receive travel reimbursement for the visit.

**Breath Alcohol Concentration:** The BrAC assessment will be administered at all study visits. The breath alcohol monitor is a handheld device that uses a disposable mouthpiece and reports the concentration of alcohol in exhaled breath. Any reading > 0.000 indicates alcohol consumption within the last 14 hours. Participants with a BrAC greater than or equal to 0.01 at the Intake Visit will be ineligible. Participants who have a BrAC reading greater than or equal to 0.01 at either tDCS visit may be ineligible to continue with the visit and will only be rescheduled/allowed to proceed with the study at the discretion of the Principal Investigator.

**Demographics:** Standard surveys will collect demographics (e.g., age, education, race, and gender).

**Medical:** Height and weight will be measured and recorded. All participants will complete a medical history form with a trained staff member to review for all contraindications listed previously.

**Shipley Institute of Living Scale:** All participants will complete the Shipley Institute of Living Scale (SILS) at the Intake Visit. The scale consists of two subtests: a 40-item vocabulary test and a 20-item test of abstract thinking. The total administration time is 20 minutes (10 minutes per subtest). A trained member of the study staff will score

2012; Roche et al., 2014). Similar models were used to estimate the effects of dose group on total number of days of biochemically-verified abstinence during the monitored abstinence period; age, sex, race, and nicotine dependence (FTND score) were included as covariates.

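### Does the craving rating at the end of each tDCS session come too late, and after too much smoking, to be worth keeping as planned?

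*Combined protocol and SAP*

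**What the plan says.** The sequence is set out under Study Procedures, 1. Procedures.

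- **Before stimulation** (tDCS Sessions, list of assessments before the tDCS period, item 4), after about 18 hours without smoking: "Paper and pencil questionnaires (brief QSU-B, G-FCQ-S, smoking TLFB").
- **Resist period** (Craving and Smoking Assessment, step 2): "Eight cigarettes of their preferred brand will be placed in view on a table in the lab room". The period lasts 50 minutes, smoking is allowed at any time, and each 5-minute delay earns money. The headgear stays on throughout, but "the stimulation will only be delivered for the first 20 minutes".
- **Ad-lib period** (step 3): 60 minutes, with a small charge for each cigarette lit. This step names latency to first cigarette and number of cigarettes as the primary outcomes.
- **Step 4:** "all participants will be asked to smoke one cigarette in order to standardize smoke exposure for subsequent tasks".
- **Step 5:** "Participants will complete paper and pencil assessments of craving and a tDCS side effects questionnaire". The craving instrument is not named.
- **Monitoring visits** on Days 6, 8, 10 and 12: "Complete measures of smoking urges (Table 1").

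Table 1 lists "Urges/Cravings (QSU-B") as an intermediate outcome at Intake, at Sessions 1-3 and at the monitoring visits. It does not separate before from after within a session. The section headed Screening/Covariates breaks off in the Shipley description ("A trained member of the study staff will score") and resumes at the tail of the analysis text, so the descriptions of the outcome measures cannot be read.

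**The concern.** If tDCS reduces craving, the natural time to look is during stimulation or soon after it. The visible text has no craving rating in that window. The one within-session rating after stimulation has three weaknesses for this purpose.

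1. It is late.
2. Everyone has just been asked to smoke, which should lower craving in all arms and compress any difference between them.
3. It follows smoking that participants chose and that the treatment may have changed. If active stimulation helps people resist, that arm reaches step 5 having smoked less and may report more craving, which would offset a real benefit. Adjusting for the amount smoked would not solve this, because it conditions on something that happens after randomisation.

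Step 4 gives everyone the same most recent exposure, but it does not equalise the total smoked. What is at stake is interpretation: a null result on this rating could be misread as showing that tDCS has no acute effect on craving.

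**Working it through.** The plan states no sample size, power or timing figure for craving, so there is nothing of its own to reproduce. The check is the session clock, followed by a comparison with the alternative.

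**Session clock.** Inputs are the 20 minutes of current from minute 0, the 50-minute resist period and the 60-minute ad-lib period.

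- Smoking opportunity before step 4: 50 + 60 = 110 minutes.
- Current off to end of ad-lib period: 110 − 20 = 90 minutes. Step 5 is later still, by the time taken to smoke the requested cigarette.
- Cigarettes before step 5: 0-8 chosen plus 1 requested = 1-9. This assumes that the eight cigarettes serve both periods and that the request is followed. The ad-lib payment also fits eight cigarettes ($4.00 / $0.50 = 8), but the text does not say whether the table is restocked.

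**All craving ratings, if step 5 uses the QSU-B.** Intake 1 + pre-session 3 + step 5 3 + monitoring 4 = 11. After the first stimulation there are 3 + 2 + 4 = 9. The six outside step 5 fall 2 days (before Sessions 2 and 3) and 1, 3, 5 and 7 days (monitoring) after the latest stimulation. So no visible rating falls within 90 minutes of current off. The six can show carry-over, although craving at the monitoring visits also depends on whether the person has lapsed.

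**How weak is weak?** This is an illustration on assumed inputs. Suppose an effect that would be detected with 80% power when first present (two-sided 5%, standardised effect 1.96 + 0.84 = 2.80) and a fraction f of it surviving to step 5. Power is approximately Φ(2.80f − 1.96) + Φ(−2.80f − 1.96).

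| f | Power |
|---|---|
| 1 | 0.80 |
| 0.75 | 0.56 |
| 0.5 | 0.29 |
| 0.25 | 0.11 |

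The documents give no value for f. Power is reduced but not zero.

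**Would a rating at minute 50 be better?**

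| | Step 5 | Minute 50 |
|---|---|---|
| After current off | at least 90 min | 50 − 20 = 30 min |
| Smoking opportunity before it | 110 min | 50 min |
| Cigarettes before it | 1-9 | 0-8 |
| Same most recent exposure for all | yes (step 4) | no |

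Delay improves. Mixing with smoking does not clearly improve. If each cigarette lowers craving by b SD, a true effect of f × d is cancelled when the active arm has smoked k = f × d / b fewer cigarettes. Take d = 0.45, the design effect size in the futility paragraph, only as a scale, since it is not stated for craving.

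- Step 5 with f = 0.5: k = 0.225 / b, which is 2.25 cigarettes at b = 0.1 and 0.75 at b = 0.3.
- Minute 50 with the whole effect intact (f = 1): k = 0.45 / b, which is 4.5 at b = 0.1 and 1.5 at b = 0.3.

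The same bias operates at minute 50, with a larger margin only on the assumption that more of the effect remains and b is unchanged. Without the step 4 cigarette, b may well be larger there: people who have just smoked would be compared with people about 18 hours plus 50 minutes abstinent, roughly 19 hours.

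**The case for a change.** The best case for a change is that a QSU-B at minute 50 is cheap. Staff are already giving the ad-lib instructions at that point, the resist period is over, and the rating would come 30 rather than 90 minutes after the current stops and before the requested cigarette. The facts in that argument are right, and the delay in the present schedule is real.

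Three things weigh against it.

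- It keeps the main flaw, because the minute-50 value also follows self-chosen smoking that may differ by arm.
- It is not free of effect on the primary outcomes. A craving questionnaire immediately before the ad-lib period could prompt smoking and alter the ad-lib count. The Design section describes three identical sessions, so participants would expect the questionnaire from Session 2 onward, and resist behaviour could shift too. A rating during stimulation or just before the first cigarette would avoid the mixing, but would interrupt the resist task itself. The plan says it follows a developed and validated paradigm, and altering that to improve an intermediate measure is a matter of preference.
- For this trial it comes too late. The futility paragraph reports conditional power of 0.13, below the 20% threshold, from data already collected.

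What stands is that step 5 should name its instrument and that the rating should be interpreted with care. The first is a detail that the unreadable measures text may supply, and Table 1 already points to the QSU-B. The second guards against an inference that no visible passage draws: the visible analyses concern days abstinent and the futility comparison, not a step 5 test of acute craving.

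**Conclusion.** The timing is as described: at least 90 minutes after current off, after 110 minutes of permitted smoking and after a requested cigarette. The step 5 rating is best understood as craving after smoking, and step 4's stated purpose of standardising exposure is consistent with that use. It is a weak measure of an acute tDCS effect, but the visible plan does not rely on it for one. Latency, cigarettes smoked and days of confirmed abstinence are unaffected.

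No change to the plan is needed. Keeping the behavioural task undisturbed, at the cost of a clean acute craving rating, is a fair trade-off, and the unnamed instrument is a gap that analysts can fill sensibly. A report of step 5 craving should describe it as a post-smoking rating and not take a null as evidence of no acute effect. A minute-50 rating is an option for future use of the paradigm, but it should not be presented as a clean acute measure.

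This rests on the readable text. The outcome-measure descriptions are missing and could contain further ratings. The power and cancellation figures are illustrations on assumed inputs, and the conclusion does not depend on them.

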A second study exploring the safety of the technique was reported by Iyer and colleagues (Iyer, Mattu et al. 2005). These investigators report experience with 103 subjects from age 19-70 (mean  $37.5 \pm 12.9$ ); half of the participants received sham treatment. In this study, a current density of  $40 \text{ microA/cm}^2$  for 20 minutes was administered to approximately 36 participants and a current density of  $80 \text{ microA/cm}^2$  was used for 15 participants. One electrode was placed over the left frontal region and the other over the right supraorbital region. EEG was recorded in 9 participants. No participant asked to stop the protocol and no participant reported significant pain. Some participants noted mild tingling at the electrode site. Minor redness was noted under the electrode site in two men who had recently shaved their heads. Cognitive function was assessed before and after stimulation. With  $80 \text{ microA/cm}^2$  current density a significant improvement in verbal fluency was observed with anodal stimulation but not in the sham or cathodal stimulation groups. A battery of neuropsychological tasks was administered to screen for adverse effects. No adverse effects were found for any measure of cognitive performance.

Finally, Poreisz and colleagues (Poreisz, Boros et al. 2007) reported on their extensive experience (567 sessions) with tDCS to multiple brain regions in 102 healthy participants and patients. None of the participants asked for a session to be terminated or required any medical assistance. For this study all participants completed a questionnaire inquiring about potential adverse effects. The questionnaire included assessment of headache, difficulties in concentrating, mood changes, visual perceptual changes and uncomfortable sensations (e.g., tingling, burning). Responders included healthy participants (75.5%), migraineurs (8.8%), post-stroke patients (5.9%) and patients with tinnitus (9.8%). A mild tingling sensation was the most common symptom, occurring in 71% of participants; the mean rating of the tingling was  $1.74 \pm 0.84$  on a 1-5 scale. Moderate fatigue was noted in 35% of participants during but not after the stimulation; the mean rating was  $2.17 \pm 1.11$ . Itching under the electrode was reported by 30%; the mean rating was  $1.6 \pm 0.72$ . Burning was reported by 22% and pain by 16% but, once again, both were regarded as quite mild ( $1.59 \pm 0.91$  and  $1.41 \pm 0.71$ , respectively).

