There have been no significant side effects noted in any study involving tDCS to date. That is to say that in the approximately 300+ studies that have been published to date there have been no reported seizures, loss of consciousness or persistent neurologic signs or symptoms. Moreover, there have been 15 studies in which tDCS has been administered to stroke patients, again with no significant side effects. These data are in accord with our collaborator laboratory's observations. In the approximately 200 sessions [name] laboratory has performed with normal healthy participants there have been no significant side effects. In short, all existing evidence indicates risks posed by tDCS are non-significant. In the unlikely event that either the participant or the person administering tDCS has significant concerns, the participant will be escorted to the Emergency Room if a physician involved with the study cannot be contacted immediately. A physician involved with the study will then contact the participant within 24 hours to follow up.

All personnel using tDCS will be properly trained in the research protocol to ensure safe handling of the equipment. The training protocol includes hands-on training, written examination, mandatory observation of tDCS delivery and mandatory administration of tDCS under observation by a trained staff member.

**Nicotine Withdrawal:** Many individuals who stop smoking exhibit a pattern of symptoms related to withdrawal from tobacco use. These symptoms include: sadness and anxiety, irritability, anger, difficulty concentrating, appetite change and weight gain, insomnia, and decreased heart rate. Eliminating the risk for these would not be possible, although in most cases these events are short-lived and have low intensity. The study personnel will be trained to recognize these symptoms and educate the participants about them (e.g., duration, methods for reducing them).

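### No side-effect question is scheduled after the Day 5 session, although participants attend four more visits up to Day 12

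*Combined protocol and SAP*

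**What the plan says.** Under Study Procedures, the schedule is stated as follows: "Participants will complete stimulation sessions on Days 1, 3, & 5". Within each session the current runs only at the start of the 50-minute resist period: "the stimulation will only be delivered for the first 20 minutes". The next step is "After 50 minutes (regardless of whether the participant decided to smoke during the resist period), the 60 minute ad-lib smoking session will commence". After a standardising cigarette comes item 5 of Craving and Smoking Assessment: "Participants will complete paper and pencil assessments of craving and a tDCS side effects questionnaire".

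The questionnaires listed before stimulation are "Paper and pencil questionnaires (brief QSU-B, G-FCQ-S, smoking TLFB". None of these is a side-effect measure. Staff also check before each session that eligibility has not changed.

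For the Monitoring Visits on Days 6, 8, 10 and 12, the listed tasks are "Complete CO, smoking rate (TLFB), and concomitant medication assessment", plus measures of smoking urges. Table 1 has a Side effects row with a mark under tDCS Sessions 1-3 and none under Monitoring Visits 1-4.

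Three other places bear on safety. Potential Study Risks says in general terms that adverse reactions will be assessed and reported. The same section provides emergency escort and physician contact within 24 hours when a significant concern is raised. Data and Safety Monitoring assigns ongoing oversight to the investigator, staff and IRB.

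**The concern.** A questionnaire completed about an hour and a half after stimulation captures immediate sensations. It cannot show whether they resolved, or whether something appeared that evening or the next day. For Sessions 1 and 2 there is at least a later session at which a participant might mention it. After Session 3 there is no further scheduled question, although staff see the participant four more times.

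The effects at issue are mostly mild ones, of the kind participants may not volunteer. The protocol's own literature summary includes, for example: "Minor redness was noted under the electrode site in two men who had recently shaved their heads". Spontaneous reporting tends to be less complete than direct questioning and gives no proper denominator. A comparison of 1 mA, 2 mA and sham for effects beyond the session day would therefore rest on whoever happened to speak up. The same section draws reassurance from the absence of lasting effects in earlier studies: "there have been no reported seizures, loss of consciousness or persistent neurologic signs or symptoms". As scheduled, this trial would add little systematic evidence on that question.

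**Working it through.** The plan gives no figure to reproduce. The check compares the session procedures, the monitoring-visit list and Table 1, with simple arithmetic on the stated times.

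**Timing of the last questionnaire**
- Resist period: 50 min. Ad-lib period: 60 min. Stimulation: the first 20 min of the resist period.
- Start of stimulation to end of the ad-lib period: 50 + 60 = 110 min.
- End of stimulation to end of the ad-lib period: 110 - 20 = 90 min. The standardising cigarette comes next, so the questionnaire falls a little later than this.

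**Coverage of visits after randomisation**
- tDCS sessions (Days 1, 3, 5): 3 of 3 have a side-effect item.
- Monitoring Visits (Days 6, 8, 10, 12): 0 of 4.
- In total: 3 of 3 + 4 = 7 visits.

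**Time from the last stimulation to each later visit**
- 6 - 5 = 1 day, 8 - 5 = 3 days, 10 - 5 = 5 days, 12 - 5 = 7 days. No side-effect question is scheduled at any of them.

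**Later opportunities for the earlier sessions**
- Session 1: questionnaires on Day 3 (2 days later) and Day 5 (4 days later).
- Session 2: questionnaire on Day 5 (2 days later).
- Session 3: none.

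**Does other text fill the gap?**
- The adverse-reaction statement names no visit, instrument or collection window.
- The 24-hour physician contact begins only once someone has a significant concern.
- The data and safety monitoring section covers record checks and oversight, not questions put to participants.
- Concomitant medication is recorded at all four Monitoring Visits and could reveal a treated symptom, but not an untreated one.
- Table 1 also lists a Post-Test Questionnaire after Session 3 only. Whatever it contains, it is a session-day measure.

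**The case against.** The best defence is that safety information does not stop on Day 5. Medication is recorded at every later visit, staff can hear spontaneous reports, the general commitment on adverse reactions has no end date, and there is a route for significant concerns. This stands. A reader might infer that nothing is collected after Day 5, or that later effects cannot be detected. The documents support neither. What is missing is solicited, uniform collection.

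A reader might also infer that effects between sessions are missed. That goes too far. Participants return on Days 3 and 5, staff recheck eligibility (the criteria include medical conditions that could compromise safety, and recent seizure), and the questionnaire is given again. Its recall window is not visible, because the supplied text breaks off within the measures descriptions.

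A third tempting reading is that the trial's own exposure figures require longer follow-up. The stated 2 mA maximum at 25 cm² exceeds the human bounds quoted from the safety review: 0.08/0.02875 = 2.8 for density and 0.096/0.022 = 4.4 for charge. With the 5x7 electrode, taken as 35 cm², the ratios are 2.0 and 3.1. Zero serious events among the 15 people cited at 80 microA/cm² would give a one-sided 95% upper bound of 1 - 0.05^(1/15) = 18%. None of these figures concerns delayed onset or duration, so they do not carry the point. The risk section likewise reports that persistent neurologic signs have not been seen; it does not name them as an expected risk.

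Finally, Days 6 to 12 are the quit attempt, when withdrawal itself produces sadness, anxiety and poor concentration. Individual answers will be hard to attribute to stimulation. This is a real limitation, only partly offset by having a randomised sham arm attend the same visits.

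**Conclusion.** The point holds as a gap in solicited follow-up. Three of three sessions and none of the four later visits have a side-effect item, the last record coming about 90 minutes after the final stimulation ends. For the 7 days from Day 5 to Day 12, new or continuing effects depend on unsolicited reporting, medication entries or the significant-concern route.

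This is a low-cost improvement, not a contradiction in the plan. It does not affect the primary outcomes, and it is not evidence of harm. It rests on two assumptions: that Table 1 and the monitoring-visit list are complete, which their agreement supports, and that no side-effect assessment at the Monitoring Visits is described in the part of the measures text that is not visible.

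**What to change.** 1. Give the existing tDCS side effects questionnaire at the Monitoring Visits on Days 6, 8, 10 and 12.
2. At Sessions 2 and 3, include a question on effects since the previous session, so that the recall period is explicit.
3. Extend the Side effects row of Table 1 to Monitoring Visits 1-4, with a footnote for the added question at Sessions 2 and 3.
4. Summarise new and ongoing effects by arm against sham. Read mood and concentration items only as a comparison between randomised arms, because they overlap with withdrawal.

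The cost is a protocol and Table 1 edit, a few minutes per visit (the Monitoring Visits last about 20 minutes) and slightly more data entry. No new visit or instrument is needed.

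The statistical text already reports a futility analysis, so follow-up may be complete. In that case, state in the safety report that solicited side effects cover session days only, and that anything after Day 5 comes from unsolicited sources.
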